they were taught they are actually treating patients by stimulating ear acupoints and that the aim of the study was to compare the efficacy and safety of acupuncture administered by an experienced acupuncturist as compared to acupressure administered by unexperienced medical staff after a short training. Patients were told they are receiving ear-point stimulation. Therefore, this study arm was double blinded. SOC was administered as well as described earlier.

Outcomes:

The primary outcome was dyspnea intensity pre- and post-treatment in the 4 days of follow-up. It was measured daily, before and one hour after treatment (for acupuncture and sham-control groups) or after first evaluation (for SOC-control group), via the modified Borg (mBorg) scale, which is a validated scale that has been used to evaluate the degree of dyspnea (0- no dyspnea, to 10- worse dyspnea) in both stable COPD and AECOPD.^{21,22} Dyspnea intensity was chosen as primary outcome since it has been shown to predict clinical outcomes in AECOPD.²³

Secondary outcomes included:

Variation of clinical symptoms: Including cough intensity and sputum production associated with the AECOPD, as evaluated on a Visual Assessment Scale from 0 (no symptom) to 10 (maximally symptomatic), throughout the 4 days of evaluation.

Variation of physiologic features: Venous blood gases (pH and pCO₂) and oxygen saturation were measured before intervention and daily in the four evaluation days. Respiratory rate (RR) was measured daily, before and one hour after treatment (for true acupuncture and sham-control groups) or after first evaluation (for SOC-control group).

Treatment failure: Defined as death during hospitalization or need for noninvasive or mechanical ventilation. Treatment failure incidence was evaluated and compared between the three groups.

Duration of hospitalization: Evaluated and compared between the three study arms.

Safety: Acupuncture-related side effects were systematically evaluated after treatment in the true acupuncture group via the validated Acup-AE questionnaire administered to the patient by the acupuncturist immediately after therapy.²⁴

Minimal sample size: In a previous study evaluating the efficacy of acupuncture vs sham-acupuncture in 68 patients with chronic COPD (34 patients in each group), a 3.6±1.9 units improvement in dyspnea (according to mBorg scale) was found in the acupuncture arm, as

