Statistical analysis: Demographic and clinical data was analyzed at baseline to measure the balance among the study groups. Quantitative variables were described using mean \pm standard deviation or median and 25th-75th percentiles (Q1, Q3) depending on their distribution. Qualitative variables were described using frequency and percentage distributions. Next, we showed that our variables distribute equally between the study groups. For comparing normally distributed variables between our study groups, we used the ANOVA test. For comparing variables that do not distribute normally between our study groups, we used the Kruskal-Wallis test with adaptation to pairwise comparison. For comparing qualitative variables between our study groups, we used the independent Chi-square test and Fisher exact test. Bonferroni adjustment was used for multiple comparisons for each independent comparison of true acupuncture vs sham-control, true acupuncture vs SOC-control and sham-control vs SOC-control. Since the variation of dyspnea intensity between day 1 and day 2 had a normal distribution, a multivariate linear regression analysis was performed after collinearity, interaction and confounding analysis, in order to neutralize the effect of the different sociodemographic and medical covariates on the primary outcome in the 3 study arms. The adjusted unstandardized regression coefficients were given with confidence interval (CI), while

a $p < 0.05$ was considered as statistically significant. Data analysis was performed using IBM SPSS version 22 statistics software.

Results:

Baseline patient data: 104 patients were screened for eligibility from November 2017 to February 2020. Among them, 72 met inclusion criteria and were recruited. Twenty-six of them were assigned to the true acupuncture arm, 24 to the sham-control arm, and 22 to the SOC-control arm. Baseline demographic and clinical characteristics were similar in patients from the 3 study arms as shown in Table 1. To note, all the patients randomized to any of the three groups completed treatments per-protocol (Fig. 1).

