Primary outcome: Baseline dyspnea was similar in the three groups. A statistically significant difference between the three groups in dyspnea intensity was found from the first day of evaluation after treatment (median [Q1, Q3] mBorg score 5.0 [4.0, 5.0] in true acupuncture, 6.0 [4.25, 7.875] in sham-control and 7.5 [5.5, 8.0] in SOC-control, $p=0.014$ – significant difference of both true acupuncture vs sham-control: $p=0.031$, and true acupuncture vs SOC-control: $p=0.014$, but non-significant between sham-control and SOC-control: $p=0.34$), and until day 3 after treatment (Fig. 2A). After adjustment for such covariates in a multivariate linear regression analysis, the association of study arm with improvement of dyspnea from day 1 to day 2 remained statistically significant (Table 2).

Secondary outcomes:

- Patient-reported outcomes:

Baseline VAS scores for cough and sputum intensity were similar in the three study arms (Table 1). No statistically significant difference in the cough intensity was observed between the three study arms throughout the 4 days of follow-up (Fig. 2). However, a statistically lower level of sputum production was observed in the true acupuncture arm as compared with sham-control and SOC-control from day 2 ($p=0.04$) (Fig. 2). Post-hoc analysis showed a statistically significant difference between true acupuncture and sham-control in day 2 ($p=0.024$), day 3 ($p=0.010$) and day 4 ($p=0.018$), while only on day 2 between true acupuncture and SOC-control ($p=0.044$), and no statistically significance between sham-control and SOC-control.

- Physiologic assessment:

Baseline physiologic data were similar in the three groups (Table 1). A statistically significant difference was observed in respiratory rate (RR) at day 2 after treatment ($p=0.002$), with significant difference both between true acupuncture and sham-control ($p=0.005$) and between true acupuncture and SOC-control ($p=0.003$), but not between sham-control and SOC-control

($p=0.050$), while all other RR measurements were statistically similar between the 3 arms throughout the 4-day follow-up (Fig. 3A).

Concerning pH, a statistically significant difference was observed at day 4 between the 3 groups ($p=0.048$), although post-hoc analysis did not show any statistical significance when comparing groups head-to-head (Fig. 3C).

No statistically significant difference was observed when comparing other physiologic measures between the 3 study groups (Fig. 3).

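### Repeatedly measured secondary outcomes are tested reading by reading at p<0.05, corrected only across arm pairs, so the plan cannot tell a sustained effect from a chance day

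*Combined protocol and SAP*

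**What the plan says.** **Measurement (Methods, Outcomes).** The symptom outcomes are described as "Including cough intensity and sputum production associated with the AECOPD", rated "throughout the 4 days of evaluation". Venous pH, pCO2 and oxygen saturation have a reading before the intervention and one on each of four days. RR is read twice a day for four days. Treatment failure and length of stay are each compared once.

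**Testing (Methods, Statistical analysis).** The threshold is given as "a $p < 0.05$ was considered as statistically significant". The only multiplicity rule reads: "Bonferroni adjustment was used for multiple comparisons for each independent comparison of true acupuncture vs sham-control, true acupuncture vs SOC-control", and it goes on to name the third pair. No hierarchy, no repeated-measures model, and no correction across days, readings or outcomes is described.

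**Reporting (Results, Secondary outcomes).**
- RR: "A statistically significant difference was observed in respiratory rate (RR) at day 2 after treatment" (p=0.002), "while all other RR measurements were statistically similar between the 3 arms throughout the 4-day follow-up".
- Sputum: lower with acupuncture from day 2 (p=0.04). Acupuncture against sham gives 0.024, 0.010 and 0.018 on days 2, 3 and 4. Acupuncture against standard of care is significant on day 2 only (0.044).
- pH: "Concerning pH, a statistically significant difference was observed at day 4 between the 3 groups" (p=0.048). The same sentence adds that no pair of arms differed.
- Cough, pCO2 and saturation: no significant difference.

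**The concern.** Each extra day or reading is another chance to cross 0.05, and the stated correction covers only the arm pairs within one reading. A reader who is told that RR differed at one reading, or that sputum differed from a certain day, cannot learn from the plan whether this is a sustained effect or the reading that happened to cross the line.

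Day-by-day testing also ignores that the readings come from the same 72 patients. Neighbouring days are correlated, so three positive days in a row are not three independent confirmations. A joint analysis would use that correlation to give one answer per outcome. At stake is how far the secondary findings on sputum and RR can be used to support the primary result on dyspnea.

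**Working it through.** The plan gives no error rate for the secondary outcomes, so there is no figure of its own to reproduce.

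**Step 1. Number of three-arm tests.** This is an assumption built from the Outcomes section. The tests are not listed, and the figures that would show them are not available.

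| Counting rule | Cough | Sputum | RR | pH | pCO2 | Saturation | Single outcomes | Total m |
|---|---|---|---|---|---|---|---|---|
| First reading of every outcome is baseline | 3 | 3 | 7 | 3 | 3 | 3 | – | 22 |
| As above, but four days kept for gases and saturation (separate pre-intervention reading) | 3 | 3 | 7 | 4 | 4 | 4 | – | 25 |
| Every day and reading | 4 | 4 | 8 | 4 | 4 | 4 | – | 28 |
| Four days each, RR after its first reading, plus treatment failure and length of stay | 4 | 4 | 7 | 4 | 4 | 4 | 2 | 29 |

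**Step 2. Expected false positives if no effect exists** = m × 0.05.
- 22 × 0.05 = 1.1
- 29 × 0.05 = 1.45

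This expectation does not depend on correlation between days.

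**Step 3. Chance of at least one**, if tests are independent = 1 − 0.95^m.
- m = 22: 1 − 0.95^22 = 0.68
- m = 29: 1 − 0.95^29 = 0.77

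A simulation at m = 29 with equal correlation between the readings of one outcome (40,000 runs, chi-square statistics on 2 df) gave 77% at correlation 0, 71% at 0.5 and 59% at 0.8. The correlations are assumptions.

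**Step 4. Bonferroni across readings within one outcome**, applied to the reported three-arm p-values.
- RR: 0.002 × 8 = 0.016
- pH: 0.048 × 4 = 0.192
- Sputum: only p=0.04 is given, attached to day 2; 0.04 × 4 = 0.16. The correction should use the smallest daily value, and the day-3 and day-4 three-arm values are not in the text. The smallest pairwise value is 0.010 (day 3, against sham). If it is already adjusted for pairs, 0.010 × 4 = 0.040. If not, 0.010 × 3 × 4 = 0.12.

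Across the whole set the threshold is 0.05/22 = 0.0023 to 0.05/29 = 0.0017. RR at 0.002 lies between the two, so it passes or fails with the count chosen.

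**Step 5. Are the sputum pairwise values already adjusted?** A Kruskal-Wallis p of 0.04 on 2 df implies H = 6.44 (6.20 to 6.70 allowing for rounding). If 0.024 were a Bonferroni-adjusted Dunn value, the raw p would be 0.024/3 = 0.008, with squared z = 7.03. A Dunn squared z cannot exceed H for the same data. So 0.024 is either unadjusted or from another pairwise test. If the sputum values are unadjusted, multiplying by three gives:

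| Comparison | Reported | × 3 |
|---|---|---|
| Day 2, against sham | 0.024 | 0.072 |
| Day 3, against sham | 0.010 | 0.030 |
| Day 4, against sham | 0.018 | 0.054 |
| Day 2, against standard of care | 0.044 | 0.132 |

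**The case against.** The outcomes are labelled secondary, below a named primary. The Results say openly that the other RR readings did not differ and that the pH difference had no pair behind it. No discussion or conclusion in the document builds a claim of benefit on pH. All of this stands.

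Three stronger readings are tempting, and the documents do not support them.

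- *A reader might infer that sputum on day 2 and pH on day 4 are isolated positives presented as effects.* Sputum is below 0.05 against sham on three consecutive days; only the comparison with standard of care is confined to day 2. pH is called statistically significant but is qualified at once, and no direction is stated. The isolated positive is RR.
- *A reader might infer that only RR would survive correction.* This cannot be shown. The day-3 and day-4 three-arm values for sputum are not given, and the answer turns on whether 0.010 is already adjusted (0.040 or 0.12).
- *A reader might infer that the positives are simply the expected chance findings.* The text reports three (RR, sputum, pH), and there would be five if sputum also passed the three-arm test on days 3 and 4. At m = 29 with no effect, the chance of three or more is about 17-22%, and of five or more about 1-7%, over correlations 0 to 0.8. Chance is a live explanation, not an established one.

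The test count is also soft, and independence is implausible for repeated readings. That lowers the chance of at least one false positive but leaves the expected number unchanged.

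**Conclusion.** The concern holds as a gap in the analysis rule. Secondary outcomes are tested at each reading at 0.05, correction is stated only across arm pairs, and nothing separates a sustained effect from a chance day.

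On an assumed 22 to 29 tests, about 1.1 to 1.45 false positives are expected under no effect. The chance of at least one is 68-77% under independence, and 59-71% at m = 29 with within-outcome correlation 0.8 to 0.5.

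The three reported findings differ in strength. RR withstands correction for its eight readings (0.016) but is borderline across the full set. pH does not withstand correction for four days (0.19). Sputum is undecided on what is reported. The primary outcome is not touched by this point, and it does not show that any secondary finding is false. The change should be made, because sputum and RR are the secondary results most likely to be cited in support of the primary.

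**What to change.** For each of the six repeated secondary outcomes, replace the day-by-day tests with one repeated-measures analysis containing arm, reading, arm-by-reading and the baseline value. Where the outcome is not normal, use a transformed or rank-based version, in keeping with the plan's own use of Kruskal-Wallis for such variables.

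- Define the single test as the arm effect averaged over the post-baseline readings, followed by the three Bonferroni-adjusted arm contrasts.
- Show reading-level estimates with intervals as descriptive, without significance claims.
- Label the secondary set exploratory. Label this reanalysis post hoc, since the results are already known.
- State how many tests were run, and which reported pairwise p-values are already Bonferroni-adjusted.

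The cost is six model fits on existing data and revised wording. There will probably be fewer nominally significant secondary results. An averaged test also has less power for a difference confined to one reading, so the RR finding may weaken.

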- *Treatment failure:*

No death or mechanical ventilation occurred in the study participants during follow-up. However there had a total of 4 treatment failures, all of them were non-invasive ventilations, which occurred in 2 (8%) patients in the true acupuncture arm, 1 (4.3%) in the sham-control arm and 1 (5%) in the SOC-control arm ($p=0.83$).

- *Duration of hospitalization:*

No difference was noted in terms of duration of hospitalization between the three study arms (5.5 ± 2.3 days for true acupuncture vs. 6.0 ± 2.9 days for sham-control and 6.3 ± 2.9 days for SOC-control, $p=0.050$).

- *Safety:*

No side effect of acupuncture treatment was reported during the study period as assessed by the Acup-AE questionnaire.

Tables and Figures:

Table 1: Baseline characteristics

[figure not shown]
Characteristics	True acupuncture (N=26)	Sham-control (N=24)	SOC-control (N=22)	p
Age (mean ± SD)	69.2±10.1	70.7±8.1	67.4±9.3	0.47
Gender (Men)	20 (77%)	15 (62%)	17 (77%)	0.43
Comorbidities				
Cardiovascular	18 (69%)	20 (83%)	15 (68%)	0.42
Respiratory (other than COPD)	7 (27%)	2 (8%)	5 (23%)	0.23
Gastroenterological	2 (8%)	4 (17%)	5 (23%)	0.34
Renal / Urologic	7 (27%)	3 (12%)	5 (23%)	0.44
Metabolic / Endocrinological	15 (58%)	13 (54%)	13 (59%)	0.94
Hematological / Oncological	3 (12%)	6 (25%)	3 (14%)	0.40
Neurological	4 (15%)	0 (0%)	1 (5%)	0.09
Smoking status				
Smoker	13 (50%)	16 (67%)	14 (64%)	0.44
Former smoker	13 (50%)	8 (33%)	8 (36%)	
Never smoked	0	0	0	
CCI (median [Q1, Q3])	6.0 [3.5, 6.0]	5.0 [4.0, 6.75]	4.5 [3.0, 7.25]	0.87
COPD severity				
Mild: FEV1 ≥ 80%	1 (4%)	0 (0%)	1 (5%)	
Moderate: 50% ≤ FEV1 < 80%	4 (15%)	5 (21%)	5 (23%)	0.69
Severe: 30% ≤ FEV1 < 50%	7 (27%)	11 (46%)	9 (41%)	
Very severe: FEV1 < 30%	5 (19%)	4 (17%)	4 (18%)	
Unknown	9 (35%)	4 (17%)	3 (14%)	
Pulmonary hypertension				
None	10 (38%)	15 (62%)	16 (73%)	
Mild: mPAP = 25-40 mmHg	4 (15%)	3 (12%)	3 (14%)	
Moderate: mPAP = 41-55 mmHg	3 (12%)	0	2 (9%)	0.11
Severe: mPAP > 55 mmHg	0	0	0	
Unknown	9 (35%)	6 (25%)	1 (5%)	
COPD exacerbation hospitalizations				
0	19 (73%)	12 (50%)	9 (41%)	
1-4	6 (23%)	11 (46%)	9 (41%)	0.09
≥5	1 (4%)	1 (4%)	4 (18%)	
Treatment				
Inhalations	24 (92%)	23 (96%)	22 (100%)	0.41
Systemic corticosteroids	3 (12%)	3 (13%)	1 (5%)	0.61
Theophylline	0	0	1 (5%)	0.32
Oxygen home therapy	8 (31%)	12 (52%)	8 (36%)	0.29
BiPAP	4 (15%)	2 (8%)	4 (18%)	0.60
APACHE-II at admission (mean ± SD)	13.3±3.6	12.0±4.4	11.0±3.8	0.14
Baseline data (median [Q1, Q3])				

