Dyspnea (mBorg)	8.0 [5.5, 8.75]	6.5 [5.0, 8.5]	7.75 [6.0, 8.5]	0.82
Cough (VAS)	7.5 [5.0, 8.0]	5.0 [5.0, 7.4]	5.0 [3.6, 7.5]	0.35
Sputum (VAS)	6.0 [1.5, 7.5]	6.0 [4.25, 6.0]	5.0 [1.9, 6.0]	0.22
O₂ saturation				
≤ 80%	4 (15%)	1 (4%)	0	0.30
81-89%	9 (35%)	10 (42%)	10 (45%)	
≥ 90%	13 (50%)	13 (54%)	12 (55%)	
PCO₂ (mmHg)				
< 45	6 (23%)	3 (12%)	8 (36%)	
45-60	12 (46%)	17 (71%)	9 (41%)	0.10
60-80	5 (19%)	4 (17%)	5 (23%)	
> 80	3 (12%)	0	0	
pH				
< 7.2	0	0	0	
7.2-7.3	5 (19%)	4 (17%)	1 (5%)	0.30
> 7.3	21 (81%)	20 (83%)	21 (95%)	
Respiratory rate (/min) (median [Q1, Q3])	21 [16, 23.75]	22 [16.5, 26]	20 [16, 22]	0.26

Legend: CCI: Charlson Comorbidity Index; mPAP: Mean Pulmonary Arterial Pressure; SOC: Standard-Of-Care.

Table 2: Multivariate linear regression analysis on variation of dyspnea from day 1 to day 2

Factors and covariates	Adjusted unstandardized coefficient (B)	95% Confidence interval		p value
		Inferior	Superior	
Constant (Intercept)	2.088	-3.409	7.584	0.457
Study Arm				
True acupuncture	2.172	0.421	3.923	0.015
Sham-control	0.390	-1.319	2.099	0.655
SOC-control	0	-	-	-
Cardiovascular comorbidities (0=No, 1=Yes)	-0.322	-2.935	1.391	0.713
Gastroenterological comorbidities (0=No, 1=Yes)	4.703	2.527	6.879	<0.001
Hospitalizations for COPD in the last year	-0.379	-0.756	-0.003	0.048
Age	-0.040	-0.133	0.053	0.400
APACHE-II	0.118	-0.099	0.336	0.287
Charlson Comorbidity Index	-0.026	-0.406	0.354	0.894

Figure 1: Flow-chart

Legend: SOC: Standard-of-care.

Figure 2: Between-group comparison of patient-reported outcomes

[figure not shown]

Figure 3: Between-group comparison of physiologic features

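### The printed length-of-stay p-value of 0.050 does not fit the printed means and SDs, which give about 0.58 by one-way ANOVA

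*Combined protocol and SAP*

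**What the plan says.** Under Results, Duration of hospitalization, the text states "No difference was noted in terms of duration of hospitalization between the three study arms" and gives 5.5 ± 2.3 days for true acupuncture, 6.0 ± 2.9 for sham-control and "6.3 ± 2.9 days for SOC-control, $p=0.050". The test is not named.

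The Statistical analysis section offers two candidates: "For comparing normally distributed variables between our study groups, we used the ANOVA test" and "For comparing variables that do not distribute normally between our study groups, we used the Kruskal-Wallis test". The same section says that a variable's distribution decides whether it is summarised by mean ± SD or by median and quartiles, and it sets significance at p < 0.05. Baseline patient data gives arm sizes of 26, 24 and 22 and reports that all randomized patients completed treatment.

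**The concern.** The three means span 0.8 days and the SDs are 2.3 to 2.9 days. With about 24 patients per arm, differences that small relative to the spread should give a p-value nowhere near 0.05. The printed value also lies exactly on the significance threshold, so a reader will take the outcome as a near miss in favour of acupuncture when the summary data show no signal. The figure could then be repeated in later summaries of the evidence.

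**Working it through.** **Inputs.** Means 5.5, 6.0, 6.3 and SDs 2.3, 2.9, 2.9 (Results, Duration of hospitalization); n = 26, 24, 22 (Results, Baseline patient data).

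**One-way ANOVA from summary statistics.**

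- Grand mean = (26×5.5 + 24×6.0 + 22×6.3)/72 = 425.6/72 = 5.911.
- Between-arm sum of squares = 26×(0.411)² + 24×(0.089)² + 22×(0.389)² = 7.91; mean square = 7.91/2 = 3.96.
- Within-arm sum of squares = 25×2.3² + 23×2.9² + 21×2.9² = 132.25 + 193.43 + 176.61 = 502.29; mean square = 502.29/69 = 7.28.
- F(2,69) = 3.96/7.28 = 0.543, p = 0.583.

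Moving each of the six inputs by up to ±0.05 gives p from 0.486 to 0.676. The printed 0.050 is not reproduced.

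**Does the method reproduce what it should?** Table 1 has two other variables shown as mean ± SD: age and "APACHE-II at admission (mean ± SD").

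| Variable | F(2,69) | Recomputed p | Range over rounding | Printed p |
|---|---|---|---|---|
| Age | 0.735 | 0.483 | 0.458 to 0.509 | 0.47 |
| APACHE-II | 2.06 | 0.135 | 0.107 to 0.168 | 0.14 |
| Length of stay | 0.543 | 0.583 | 0.486 to 0.676 | 0.050 |

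Only the length-of-stay row fails.

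**Alternative explanations tried.**

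- *Missing patients.* The treatment-failure text gives "1 (4.3%) in the sham-control arm". That fits 1/23 (4.35%) rather than 1/24 (4.17%), so some denominators may be smaller than the arm sizes. With an assumed 25/23/20, p = 0.602 (0.507 to 0.692), which is further from 0.050.
- *Unequal variances.* Welch ANOVA gives p = 0.559 (0.458 to 0.659 over rounding).
- *A pairwise value printed in place of the three-arm one.* Pooled t-tests give 0.50 (acupuncture vs sham), 0.29 (acupuncture vs SOC) and 0.73 (sham vs SOC). The smallest is 0.146 one-sided and 0.876 after Bonferroni.
- *SDs that are really standard errors.* p = 0.977.
- *Kruskal-Wallis.* Means and SDs do not determine this p-value, so it was simulated on data forced to the printed moments. In 80,000 datasets (normal, lognormal, gamma, and lognormal rounded to whole days; the shapes are assumptions) none gave p ≤ 0.05. The smallest was 0.098 and the medians were 0.57 to 0.65.

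**How far off is 0.050?** F would have to reach 3.13 on 2 and 69 degrees of freedom. Since √(3.13/0.543) = 2.40, the mean differences would have to be 2.40 times as large (acupuncture vs SOC 0.8 × 2.40 = 1.9 days), or the SDs 1/2.40 = 0.417 times those printed. With the printed means and SDs, the total sample would have to be about 400 instead of 72.

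**Two other figures to check.**

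- Table 2, row "Cardiovascular comorbidities (0=No, 1=Yes"): B = -0.322, limits -2.935 and 1.391. The midpoint is (-2.935 + 1.391)/2 = -0.772, not -0.322. In the other eight estimated rows the midpoint is within 0.0005 of B. Reflecting the upper limit about B gives 2×(-0.322) - 1.391 = -2.035. The implied SE is then 1.713/1.96 = 0.874, z = 0.322/0.874 = 0.368 and p = 0.713, exactly as printed. The lower limit therefore looks like a one-digit error.
- Physiologic assessment: the day-2 respiratory-rate difference is called significant for the two acupuncture comparisons "but not between sham-control and SOC-control", and that last comparison carries the same p = 0.050. Nothing in the text shows this to be wrong.

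**The case against.** The arithmetic is not in dispute. The case on the other side concerns certainty and weight.

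- *The test is inferred.* If Kruskal-Wallis was used, the ANOVA result does not settle the matter, and the zero count in the simulation depends on the shapes chosen. With heavier skew, or shapes that differ by arm, p ≤ 0.05 did occur: 7 of 27,415 datasets in one set of simulations and 16 of 20,000 in another with a skewed lognormal. A deliberate search also built whole-day datasets with the printed means and SDs and a Kruskal-Wallis p near 0.05. This stands: 0.050 is very unlikely under that test, not impossible. But a rank test would imply data judged non-normal, and then the document's own rule calls for medians and quartiles, so the reporting needs correction either way.
- *A PDF-reading error.* It cannot be excluded for the Table 2 limit, and equally not for the length-of-stay p-value. Both should be compared with the source output.
- *The consequence is small.* Under the p < 0.05 rule, 0.050 is not significant, so the printed conclusion agrees with the recomputed one. A meta-analyst would normally pool the means and SDs rather than a three-arm p-value. This also stands, and it limits the weight of the point.
- *The two extra figures are separate matters.* They are, and they are listed only as checks.

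**Conclusion.** The concern holds. The printed 0.050 is not compatible with one-way ANOVA on the printed means and SDs, which gives 0.583 (0.486 to 0.676 over rounding). This rests on the stated arm sizes and on ANOVA being the test, as the mean ± SD display implies; confidence is high for that arithmetic only. A value of 0.50 lies inside the rounding range, so a misplaced zero is one possible cause, but nothing in the document confirms it.

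The conclusion of no difference in length of stay is unchanged, as are the primary outcome and the study-arm coefficients in Table 2. The fault is a wrong p-value on a named secondary outcome, and it should be corrected. The asymmetric interval in Table 2 is real as it reads here but concerns a covariate. The respiratory-rate p-value is not shown to be in error.

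**What to change.** 1. Rerun the length-of-stay comparison, name the test in the text, and replace the p-value (about 0.58 if ANOVA).
2. If Kruskal-Wallis was used, say so, and report medians with quartiles and the p-value from that test.
3. State the number analysed per arm for this outcome.
4. Compare the lower limit of the Table 2 cardiovascular row with the source output; -2.035 would fit the other figures in that row.
5. Confirm the respiratory-rate p-value for sham-control vs SOC-control against the same output.

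The cost is one rerun on existing data and a check of two printed figures. Design, endpoints and conduct are not affected.
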